10. STATISTICAL CONSIDERATIONS

10.1 Statistical Design

This is a multi-center, open-label, two-part prospective Phase II study of patients with relapsed or refractory FLT3-ITD mutation-positive AML. The study is designed to assess the safety and tolerability as well as the efficacy of administering CPX-351 with quizartinib, a second-generation FLT3 inhibitor.

A response rate (CR + CRi) of $\geq 50\%$ is targeted with 40% or less considered unacceptable. This is assumed to be an acceptable estimate based on CR + CRi/CRp of 48.2% reported with quizartinib monotherapy in a relapsed or refractory patient with FLT3-ITD AML (Cortes et al 2019). Of note, prior FLT3-targeting inhibitor exposure is permitted on this study. However, patients receiving a prior FLT3-targeting inhibitor were excluded in the QUANTUM-R study. Expected CR+CRi in relapsed or refractory patients receiving standard intensive or non-intensive salvage chemotherapy harboring an FLT3 mutation is 27% (Cortes et al 2019). The estimated response in those with relapsed/refractory FLT3-ITD AML receiving CPX-351 alone cannot be estimated. However, in a poor-risk EPI patient population, CR+CRi was reported as 39.3% (Cortes et al 2015). However, FLT3-ITD mutation presence was not utilized in the generation of EPI prognostication, and those with an FLT3-ITD mutation could in fact have a reduced response within all EPI risk groups. Thus, the expected response must be based upon the QUANTUM-R study of those receiving standard salvage options harboring an FLT3-ITD mutation.

In the safety lead-in, 10 patients will be enrolled to receive CPX-351 with quizartinib. If > 3 patients experience delayed neutrophil count recovery > 56 days or delayed thrombocytopenia recovery > 56 days from the first day on the study regimen, or if > 3 patients develop a non-hematologic toxicity, defined as a Grade 4 non-hematologic AE determined to be probably related to the combined treatment or a Grade 4 neutropenia, then the study will be terminated.

Assuming safety parameters are met, the first 10 patients will be followed for response in Part 2 of the study.

10.2 Sample Size Considerations

The null hypothesis that the ORR (defined as CR + CRi) is $\leq 27\%$ (Cortes et al 2019) will be tested against a one-sided exact alternative ORR of 50% at a target significance level of 0.05. A sample size of 30 evaluable patients achieves 80% power if the true ORR is $\geq 50\%$. The null

CONFIDENTIAL

STUDY DRUG: QUIZARTINIB
PROTOCOL DATE: 10 AUGUST 2020

DEVELOPMENT INNOVATIONS STUDY NUMBER: AML 48
VERSION 4.0

hypothesis will be rejected if 13 or more responses are observed in 30 evaluable patients. In order to allow for a non-evaluable rate of 10%, a total of 34 patients will be enrolled in the study.

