
Statistical Methodology:
	
A response rate (CR + CR with incomplete hematologic recovery [CRi]) of $\geq 50\%$ is targeted, with 40% or less considered unacceptable. This is assumed to be an acceptable estimate based on CR + CRi/CRp of 48.2% reported with quizartinib monotherapy in a relapsed or refractory patient with FLT3-ITD AML (Cortes et al, 2019). Of note, prior FLT3-targeting inhibitor exposure is permitted on this study. However, patients receiving a prior FLT3-targeting inhibitor were excluded in the QUANTUM-R study. Expected CR+CRi in relapsed or refractory patients receiving standard intensive or non-intensive salvage chemotherapy harboring an FLT3 mutation is 27%. The estimated response in those with relapsed/refractory FLT3-ITD AML receiving CPX-351 alone cannot be estimated. However, in a poor-risk EPI patient population, CR+CRi was reported as 39.3% (Cortes et al 2015). However, FLT3-ITD mutation presence was not utilized in the generation of EPI prognostication, and those with FLT3-ITD mutation could in fact have a reduced response within all EPI risk groups. Thus, the expected response must be based upon the QUANTUM-R study of those receiving standard salvage options harboring a FLT3-ITD mutation.
 
In the safety lead-in, 10 patients will be enrolled to receive CPX-351 with quizartinib. If >3 patients experience delayed neutrophil count recovery >56 days from the first day on the study regimen, or delayed thrombocytopenia recovery >56 days from the first day on the study regimen, or if >3 patients develop a non-hematologic toxicity, defined as a Grade 4 non-hematologic adverse event determined to be probably related to the combined treatment, or a Grade 4 neutropenia, then the study will be terminated.
 
Assuming safety parameters are met, the first 10 patients will be followed for response in Part 2 of the study.
 
The null hypothesis that the overall response rate (ORR, defined as CR + CRi) is $\leq 27\%$ will be tested against a one-sided exact alternative ORR of 50% at a target significance level of 0.05. A sample size of 30 evaluable patients achieves 80% power if the true overall response rate is $\geq 50\%$. The null hypothesis will be rejected if 13 or more responses are observed in 30 evaluable patients. In order to allow for a non-evaluable rate of 10%, a total of 34 patients will be enrolled in the study.

--	--

CONFIDENTIAL

STUDY DRUG: QUIZARTINIB
 PROTOCOL DATE: 10 AUGUST 2020

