10.3 Analysis Population

The following analysis populations will be used:

- The Safety Analysis Set is defined as all patients who received at least one dose of CPX-351 or quizartinib.
- The Efficacy Analysis Set is defined as all patients who received at least one dose of CPX-351 or quizartinib, who have an adequate baseline disease assessment, and an adequate post-baseline assessment and who discontinued due to death or PD prior to their first assessment.

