10.4.2 Efficacy Analysis

All efficacy analyses will be performed using the Efficacy Analysis Set.

The ORR is defined as the proportion of patients achieving a response of CR or CRi at the time of the recovery assessment. For ORR, point estimates and the associated 95% CIs (based on the Clopper-Pearson method) will be calculated.

For DOR, the estimate of the median based on Kaplan-Meier analyses will be reported. For EFS and OS, the estimated rates at 6, 12, and 24 months based on Kaplan-Meier analyses will be reported.

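### The rejection rule is given only as 13 responses in 30 evaluable patients, but 34 are enrolled and the analysis set is not capped at 30; the plan should say how the exact test applies at other numbers.

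*Combined protocol and SAP*

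**What the plan says.** Section 10.2 sets the null response rate (CR + CRi) at 27% or less, to be "tested against a one-sided exact alternative ORR of 50% at a target significance level of 0.05". It then says "A sample size of 30 evaluable patients achieves 80% power if the true ORR is" at least 50%, and that the null "hypothesis will be rejected if 13 or more responses are observed in 30 evaluable patients". The Statistical Methodology part of the synopsis repeats the rule: "The null hypothesis will be rejected if 13 or more responses are observed in 30 evaluable patients".

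On enrolment, Section 10.2 says: "In order to allow for a non-evaluable rate of 10%, a total of 34 patients will be enrolled in the study".

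On the analysis set, Section 10.4.2 says: "All efficacy analyses will be performed using the Efficacy Analysis Set". Section 10.3 defines that set by treatment received and adequate assessments, and adds patients "who discontinued due to death or PD prior to their first assessment". It sets no upper limit on the number. For the response rate, Section 10.4.2 lists a point estimate and a 95% Clopper-Pearson interval. It does not mention the test, and no section gives a cutoff for any number other than 30 or restricts the test to the first 30 evaluable patients.

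**The concern.** The plan gives its success criterion in two forms: a named test (one-sided, exact, 0.05, null 27%) and a count (13). They agree at 30 evaluable patients and disagree at every number from 31 to 34. If 13 of 32 patients respond, one reader can declare success because 13 was reached, and another can decline because the exact p-value is 0.066. Both can cite Section 10.2.

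The interval in Section 10.4.2 does not settle this. Read as a conventional two-sided interval, its lower limit at 13/30 is 25.5%, below 27%, although the rule rejects at that result. In an open-label trial, responses are visible while evaluability is being decided, so the criterion should not depend on which form is chosen once the number is known.

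**Working it through.** **Inputs, all from Section 10.2:** p0 = 0.27, p1 = 0.50, one-sided exact binomial test, target level 0.05, 30 evaluable patients, cutoff 13, 34 enrolled, 10% non-evaluable.

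**Formula.** For n evaluable patients and cutoff r, the rejection probability at response rate p is P(X ≥ r), with X ~ Binomial(n, p). Setting p = 0.27 gives the type I error and p = 0.50 gives the power.

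**Step 1: reproduce the plan.** At n = 30 and r = 13, the type I error is 0.0395 and the power is 0.819. A cutoff of 12 would give 0.0845, so 13 is the smallest valid cutoff. Enrolment: 30 / 0.90 = 33.3, rounded up to 34. The plan's figures stand.

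**Step 2: how often is n equal to 30?** Assume each of the 34 patients is independently evaluable with probability 0.90. Then n ~ Binomial(34, 0.90), with mean 34 × 0.90 = 30.6.
- P(n ≤ 29) = 0.25
- P(n = 30) = 0.20
- P(n ≥ 31) = 0.55

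**Step 3: the count of 13 and the valid cutoff at each n.** The valid cutoff is the smallest r with P(X ≥ r) ≤ 0.05 at p = 0.27.

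| n | P(n) | Type I error of ≥13 | Valid cutoff | Its type I error | Its power at 50% |
|---|---|---|---|---|---|
| 26 | 0.012 | 0.010 | 12 | 0.028 | 0.721 |
| 27 | 0.031 | 0.015 | 12 | 0.038 | 0.779 |
| 28 | 0.070 | 0.021 | 13 | 0.021 | 0.714 |
| 29 | 0.131 | 0.029 | 13 | 0.029 | 0.771 |
| 30 | 0.197 | 0.039 | 13 | 0.039 | 0.819 |
| 31 | 0.228 | 0.052 | 14 | 0.023 | 0.763 |
| 32 | 0.193 | 0.066 | 14 | 0.030 | 0.811 |
| 33 | 0.105 | 0.083 | 14 | 0.040 | 0.852 |
| 34 | 0.028 | 0.102 | 15 | 0.024 | 0.804 |

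**Step 4: average over n.** Weighting each n by P(n):
- constant 13: type I error 0.0498, power 0.833
- valid cutoff at the actual n: type I error 0.031, power 0.791

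**Step 5: sensitivity to the evaluable rate (assumed values).** At 93% evaluable, P(n ≥ 31) = 0.79 and a constant 13 averages 0.063. At 95% they are 0.91 and 0.073.

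**The case against.** The strongest reply is that nothing in the plan is wrong. The count is tied to 30 evaluable patients and is correct there, and the plan never says 13 applies above 30. The null, direction, method and level are all stated, and together they fix a unique cutoff at every n, so a competent analyst has little discretion.

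The size is also modest. The most likely n is 31, where the excess is 0.052 against 0.05. The largest figure, 0.102, needs all 34 patients to be evaluable, which has probability 2.8%. Averaged at the plan's 10% rate, a constant 13 meets the target. Power of 80% is claimed only at 30, and the uneven power at neighbouring n is a general feature of exact tests.

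All of this stands as a limit on the point. A reader might infer that the trial runs at a 10% error rate, or that the sample size is miscalculated; the documents support neither. A reader might also infer from the clause in Section 10.3 on early death or progression that n will certainly exceed 30. That clause is joined to the others by a plain conjunction and is hard to read literally, so it does not establish a larger n.

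What the reply does not remove is that the plan never says the named test will be run at the actual n, and Section 10.4.2 omits the test. The averaged 0.0498 depends on the assumed 10% rate and is not an error rate the plan claims; the trial will be reported at one realised n.

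**Conclusion.** The design reproduces at 30 evaluable patients. The defect is one of specification: the only explicit success threshold covers an evaluable number that arises about one time in five at the plan's own rate. At 31 to 34, about 55% of the time, the count of 13 and the stated 0.05 level give different answers when exactly 13 respond, and also at 34 when 14 respond (exact p 0.0517 against a valid cutoff of 15). The conflict is trivial at 31 and material at 32 to 34, which together have probability 0.193 + 0.105 + 0.028 = 0.33.

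The type I errors at each n follow from the plan's inputs alone. The probabilities and averages also assume independent evaluability at 90%. The matter should be settled before the efficacy analysis, because it can change the conclusion and costs little to close.

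**What to change.** In Section 10.2, Section 10.4.2 and the synopsis, state that the null is rejected if the one-sided exact binomial p-value against 27% is 0.05 or less at the actual size of the Efficacy Analysis Set. Add the cutoffs: 12 for 26–27 patients, 13 for 28–30, 14 for 31–33 and 15 for 34.

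The cost is one sentence and a small table, with no extra patients or data. There is a statistical price: average power is about 79% (76% at 31), against about 83% for a constant 13. The 80% figure should therefore be stated as applying at 30 evaluable patients.

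An alternative is to pre-specify that the test uses the first 30 evaluable patients in enrolment order, with the full set used for estimation. This keeps the published rule and power, but it leaves later evaluable patients out of the test and still needs the cutoffs for fewer than 30, which happens about 25% of the time at the plan's rate.

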10.3 Analysis Population

The following analysis populations will be used:

- The Safety Analysis Set is defined as all patients who received at least one dose of CPX-351 or quizartinib.
- The Efficacy Analysis Set is defined as all patients who received at least one dose of CPX-351 or quizartinib, who have an adequate baseline disease assessment, and an adequate post-baseline assessment and who discontinued due to death or PD prior to their first assessment.

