5. STUDY DESIGN

This is a multi-center, non-randomized, open-label, two-part prospective Phase II clinical trial in patients with relapsed or refractory FLT3-ITD mutation-positive AML. The study is designed to assess the safety and tolerability as well as the efficacy of administering CPX-351 (cytarabine:daunorubicin liposome complex) with quizartinib, a second-generation FLT3 inhibitor. The plan for administration is divided into three phases: induction, consolidation, and maintenance. Approximately 34 patients are planned to be screened and enrolled. Patient participation is expected to be 4 years.

A total of 10 patients will be enrolled in the safety lead-in. The safety lead-in portion of the study is designated as Part 1. If >3 patients experience delayed neutrophil count recovery >56 days from the first day on the study regimen, or delayed thrombocytopenia recovery >56 days from the first day on the study regimen, or if >3 patients develop a non-hematologic toxicity, defined as a Grade 4 non-hematologic adverse event determined to be probably related to the combined treatment, or a Grade 4 neutropenia, then the study will be terminated.

Assuming safety parameters are met, the first 10 patients will be followed for response in the Part 2 of the study. An additional 24 patients will be enrolled in Part 2 of the study (induction, consolidation and maintenance). All patients will be assessed for response.

Patients who fail to respond to therapy will be followed until a new therapy is instituted. . Patients who experience an AE that results in the discontinuation of study treatment will be

[figure not shown]
CONFIDENTIAL

STUDY DRUG: QUIZARTINIB
PROTOCOL DATE: 10 AUGUST 2020

DEVELOPMENT INNOVATIONS STUDY NUMBER: AML 48
VERSION 4.0

followed until resolution/stabilization for AEs attributed to the medication. Outcomes for all patients will be assessed for 24 months from the date of last treatment.

Figure 1 Study Schema

*All treatment phases follow a 28-day cycle. Induction and re-induction consist of: CPX-351 (liposomal daunorubicin 44 mg/m² IV and cytarabine 100 mg/m² IV) + quizartinib 30 mg PO QD. The maintenance phase: begin quizartinib 30 mg PO QD on Days 1-14. If there are no toxicities and QTcF is maintained ≤ 450 msec, increase dose to 60 mg QD on Day 15.

[†]For one cycle

[‡]For up to two cycles

CONFIDENTIAL

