6.4.6 Long-Term Follow-up

A formal end-of-study visit will be performed every 6 months for 2 years post-study treatment. The following procedures and tests will be done:

- Disease response assessment per CIBMTR classification (Appendix E)
- Survival status

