9.9 Overall Survival (OS)

Overall survival is defined as the time from the first date of treatment until death as a result of any cause. For OS time, patients that have not died or are lost to follow-up will be censored at the date the patient was last known to be alive or the date of last contact.

CONFIDENTIAL

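### As worded, Section 10.3 requires two near-exclusive conditions together, so the Efficacy Analysis Set is empty or nearly so; made alternatives, as evidently meant, the planned 13-of-30 test stands

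*Combined protocol and SAP*

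**What the plan says.** Section 10.3 defines two populations. The Safety Analysis Set is everyone dosed with either drug. The Efficacy Analysis Set takes dosed patients with an adequate baseline disease assessment and adds "an adequate post-baseline assessment and who discontinued due to death or PD prior to their first assessment".

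Section 10.4.2 gives the second set its reach: "All efficacy analyses will be performed using the Efficacy Analysis Set". That covers ORR (CR or CRi at the recovery assessment, with a Clopper-Pearson interval), DOR, EFS and OS. On the last two: "For EFS and OS, the estimated rates at 6, 12, and 24 months based on Kaplan-Meier analyses will be reported".

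Section 10.2 sets a one-sided exact test of a 27% null ORR against 50% at a target level of 0.05. The null "hypothesis will be rejected if 13 or more responses are observed in 30 evaluable patients". On enrolment: "In order to allow for a non-evaluable rate of 10%, a total of 34 patients will be enrolled in the study". It does not define evaluable separately.

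For survival, Section 9.9 states: "Overall survival is defined as the time from the first date of treatment until death as a result of any cause". Section 5 adds: "Outcomes for all patients will be assessed for 24 months from the date of last treatment". Section 6.4.6 adds: "A formal end-of-study visit will be performed every 6 months for 2 years post-study treatment", and lists survival status among the items collected.

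**The concern.** Membership conditions joined by *and* form an intersection. Here the two final conditions almost exclude each other, so a literal programmer would find no patients, or very few, on whom to compute the primary endpoint. An ordinary patient who was treated, assessed at Day 21 and Day 35 and found in CR fails the last condition. No other section supplies a working definition.

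The clause also decides whether patients who die or progress before any assessment count against the regimen. In a single-arm, open-label trial that should be explicit before data are seen.

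A smaller matter remains after the conjunction is corrected. Treated patients who leave before assessment for other reasons (Section 6.4.5 lists adverse events, withdrawal and loss to follow-up) would still be outside the OS analysis, although OS needs no marrow.

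**Working it through.** **1. Reproduce the plan's figures.** Inputs from Section 10.2: n = 30, cut-off 13, null 0.27, alternative 0.50, 10% non-evaluable. Let X be binomial(n, p).

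- Alpha = P(X ≥ 13 | 30, 0.27) = 0.0395. A cut-off of 12 would give 0.0845, so 13 is the smallest cut-off within 0.05.
- Power = P(X ≥ 13 | 30, 0.50) = 0.819, against 80% stated.
- Enrolment = 30 / 0.9 = 33.3, rounded up to 34.

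The sample size statement is sound.

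**2. Literal set.** Let A be an adequate post-baseline assessment and B be discontinuation for death or PD before the first assessment. Section 10.3 requires A *and* B. If both phrases mean the same first post-baseline assessment, the set has 0 members. It is non-empty only if they mean different assessments. The test needs 30.

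**3. Corrected set.** With A *or* B, the plan's own non-evaluable rate gives 34 × 0.9 = 30.6 patients expected, which matches the 30 in Section 10.2. The results in step 1 then apply.

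**4. OS.** At that rate about 34 − 30.6 = 3.4 treated patients fall outside the corrected set (assuming all 34 are dosed). The documents give no OS figure for this regimen, so assume 12-month OS of 40% to 50% in the set and 4 of 34 omitted. All-treated OS is (30s + d)/34, where s is OS in the set and d is the number of omitted patients alive (0 to 4):

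- s = 0.40: 12/34 = 35.3% to 16/34 = 47.1%
- s = 0.50: 15/34 = 44.1% to 19/34 = 55.9%

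**5. Set sizes other than 30.** Assume set size is binomial(34, 0.9). It is then exactly 30 with probability 0.197, above 30 with 0.554 and below 30 with 0.250. The exact one-sided 0.05 test gives:

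| n | cut-off | alpha at 27% | power at 50% |
|---|---|---|---|
| 28 | 13 | 0.0215 | 0.714 |
| 29 | 13 | 0.0295 | 0.771 |
| 30 | 13 | 0.0395 | 0.819 |
| 31 | 14 | 0.0226 | 0.763 |
| 32 | 14 | 0.0305 | 0.812 |
| 33 | 14 | 0.0401 | 0.852 |
| 34 | 15 | 0.0235 | 0.804 |

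Averaged over set size, alpha is 0.0307 and power 0.791. Using 13 at every size gives average alpha 0.0498 and power 0.833, but alpha of 0.052, 0.066, 0.083 and 0.102 at n = 31 to 34.

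**6. What rides on the early death/PD rule.** This applies only if group B were dropped instead of counted. The documents give no early death/PD rate, so take k = 1 to 4 as an assumption, with true ORR 27% among those at risk of being dropped.

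- 34 treated, set still reaching 30: p = 0.27 × 34/(34 − k), and P(X ≥ 13 | 30, p) = 0.049, 0.062, 0.077, 0.097.
- Set of 34 − k with its exact cut-off (14, 14, 14, 13): 0.051, 0.050, 0.048, 0.097.
- k dropped from a set of 30, exact cut-off (13, 13, 12, 12): 0.038, 0.037, 0.080, 0.078.

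**The case against.** The strongest reply is that no analyst would apply the sentence literally. The clause on early death and PD stands in a list of who is in the set, so its only sensible purpose is to bring those patients in. Section 10.2 needs about 30 of 34 patients, which only the alternative reading can supply. That is right, and it limits the point to a wording error in the definition. It does not remove the need to correct the only efficacy population in the plan.

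A reader might go further and infer that the primary test has an inflated type I error. The documents do not support that. The step 6 figures require dropping early deaths and progressions, which reverses the clause's purpose. Even then the result is mixed, and several cases stay at or below about 0.05. Section 10.4.2 also largely settles scoring: a member of the set without CR or CRi at the recovery assessment is in the denominator and not in the numerator.

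A reader might also infer that there is no decision rule when the set is not exactly 30. That overstates it. A one-sided exact test at 0.05 fixes the cut-off at any size, and even an unchanged 13 averages within 0.05.

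On OS, the reply is that the analysis is descriptive and the omitted group may be small: induction starts inpatient (Section 5.2.1.1), and the early-termination visit can include a marrow (Section 6.4.5). Some omitted patients will have withdrawn or been lost. Follow-up is also not described uniformly, since Section 5 follows non-responders only until new therapy and Section 6.4.5 has patients complete the study at PD. These points make OS secondary. They do not justify excluding treated patients whose survival time is defined.

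**Conclusion.** The Efficacy Analysis Set is wrong as written: about 0 patients literally, against the 30 that the primary test requires. It needs correcting because the primary ORR and every other efficacy analysis depend on it. Under the evident intent, the planned test stands at alpha 0.0395 and power 0.819. The potential cost of dropping early deaths and progressions is a reason to write the rule down, not evidence that the plan drops them.

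The OS point is sound but secondary. Its size rests on two assumptions, 4 omitted patients and 12-month OS of 40% to 50% in the set; the all-treated figure could then lie about 5 points below to 7 points above the set's figure at 40%, and 6 points either side at 50%. The cut-off point is a clarification only, and its averages assume independent non-evaluability at 10%.

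**What to change.** 1. **Section 10.3.** Define the Efficacy Analysis Set as all patients with at least one dose of CPX-351 or quizartinib and an adequate baseline disease assessment, who either (a) have an adequate post-baseline assessment, or (b) stopped because of death or PD before their first post-baseline assessment. State that group (b) counts as non-responders for ORR. This structure also makes clear that dosing and baseline requirements apply to both groups. Cost: wording only.
2. **Section 10.4.2 (secondary).** Report OS on all treated patients (the Safety Analysis Set). Do the same for EFS, because the Section 9.7 censoring rule already provides for patients with no response assessment. The EFS gain is limited, since living patients without an assessment are censored at the first treatment date. Cost: wording only; survival status is already collected.
3. **Section 10.2 (optional).** State that, if the set is not exactly 30, the cut-off follows from the exact one-sided 0.05 test already specified: 13 at n = 28 to 30, 14 at 31 to 33, 15 at 34. Cost: average power of 79.1%, just under the planned 80%, against 83.3% if 13 were used throughout.
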